# 6.4 Missing Data

Missingness will be assessed and tabulated by treatment group along with reasons for missingness to assess any differential missingness between the treatment arms. Patients impacted by COVID-19 that are related to study discontinuations, missing assessments, and missing visits due to COVID-19 will be created, sorted by patient number, randomized treatment and discontinuation date or visit, as applicable. All data will be listed and sorted by treatment and patient number within treatment.

The efficacy analyses relating to change from baseline will be based on all the available postbaseline measurements. For sensitivity analyses, we will perform a best-case (i.e., replacing missing by best value) and worst-case (i.e., replacing missing with worst value) scenario analyses with respect to the primary outcome and if the results match with the primary analyses, we will stop additional sensitivity analyses.

# 6.5 Multi-center Studies

This study was a multi-center study. Data will be analyzed by combining data from all study centers. No investigation of center effects is planned.

# 6.6 Multiple Testing

As a signal-seeking study, unless otherwise stated, all statistical tests will be 2-sided and conducted at the 5% level. All presented confidence intervals will be 2-sided 95% confidence intervals. No adjustment for multiplicity will be made for the primary and secondary efficacy variables.

# 7 Demographic, Other Baseline Characteristics, Medication and Protocol Deviations

7.1 Subject Disposition

The following flowchart (Figure 3) will be used to summarize the subject disposition in the study and by treatment. Numbers will be obtained based on the following CRFs: Inclusion/Exclusion, Randomization, Study Treatment Termination or Completion, and Study Termination or Completion.

Listings of the following will be provided.

- screen failures and reasons for failures
- discontinuation from study drug with reasons
- early discontinuation from study participation with reasons

### 7.2 Demographic and Baseline Variables

Demographic characteristics will be based on the information provided at the screening Visit.

The characteristics will be presented by treatment arm, genotype and overall:

- Age (years) at study entry continuous
- Sex categorical
- Childbearing potential status (female subjects only) categorical
- Race categorical
- Height (cm) at baseline continuous
- Weight (kg) at baseline continuous
- Alcohol use history categorical
- Smoking history categorical/ continuous (packs/year)

# 7.3 Medical History and Concomitant Diseases

Medical history will be defined as any clinically significant past medical conditions that ended before screening. Medical history will be summarised for the SAF by treatment arm and overall with number and percentage of subjects with at least one medical history item, and number and percentage of subjects by system organ class (SOC) and preferred term (PT). The terms will be sorted by descending frequency across all subjects of SOC and then, within SOC, by descending frequency across all subjects for PT.

Relevant AATD medical history will be based on the information provided at the screening visit. The characteristics will be presented by treatment arm and overall for the SAF. The following will be tabulated:

- Genotype of AATD
- Alpha-1 level (mg/dl)
- COPD (yes/no)
- Liver Disease (yes/no)
- Cirrhosis (yes/no)
- Augmentation Therapy (yes/no)
  - Continue augmentation therapy for study duration (yes/no)
  - Asthma (yes/no)

•

- Lung cancer (yes/no)
- Bronchiectasis (yes/no)
- CV issue in last 6 months (yes/no)
- Severe/uncontrolled CHF (yes/no)
- Supplemental oxygen use (yes/no) If yes on supplemental oxygen
  - o amount prescribed (≤1 liter/min, 2 liters/min, 3 liters/min, 4 liters/min, ≥5 liters/min)
  - o duration per day (<12 hrs/day vs 12-23 hrs/day)
  - years prescribed (0-2, 3-5, 6+)
  - Screening or Historical FEV1% predicted
- AECOPD within the last year (yes/no)

lf yes,

- Number of exacerbations
- o Number of hospitalizations related to AECOPD

Medical History ongoing at start of study will be summarised separately.

### 7.4 Medications

Prior medications will be defined as medications started 30 days or more prior to screening visit and stopped any day prior to administration of the first dose of study treatment. Concomitant medications will be defined as medications started within 30 days prior to screening visit and ongoing at or began during or after the administration of the first dose of study treatment. Specific list of medications checked (yes/no) at screening and in follow-up visits are:

- SABA
- SAMA
- LABA
- LAMA
- ICS
- Roflumilast
- AAT augmentation
- Azithromycin
- Theophylline
- NSAIDS
- Acetaminophen
- Warfarin/Coumadin
- other anticoagulant
- Clopidogrel
- Aspirin

These medications will be summarized by treatment and by visit.

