#### Type of Participant and Disease Characteristics

1. Capable of giving signed informed consent as described in [Appendix 3](#), which includes compliance with the requirements and restrictions listed in the informed consent form and in this protocol
2. Age  $\geq 18$  and  $\leq 80$  years
3. Patients with a confirmed diagnosis of AATD: Pi\*ZZ, Pi\*SZ, Pi\*null, or another rare phenotype/genotype known to be associated with either low (serum AAT level  $< 11 \mu\text{M}$  or  $< 57.2 \text{ mg/dL}$ ) or functionally impaired AAT including "F" or "I" mutations.
4. FEV1  $\geq 25\%$  predicted
5. Patients will be eligible if they are either a) are not currently receiving augmentation treatment and have not received augmentation in the 12 weeks prior to screening or b) have received weekly infusions of augmentation at 60 mg/kg for at least 12 weeks prior to screening and intend to continue augmentation through the study period.
6. Male or female sex
  - a. Male participants must agree to use a highly effective contraception as detailed in [Appendix 5](#) during the treatment period and for at least 4 days after the last dose of study treatment and refrain from donating sperm during this period
  - b. Female participants are eligible to participate if not pregnant; not breastfeeding; and at least one of the following conditions is met:
    - i. Not a woman of childbearing potential as defined in [Appendix 5](#)
    - OR
    - ii. A woman of childbearing potential who agrees to follow the contraceptive guidance in [Appendix 5](#). During the treatment phase and for at least 4 days after the last dose of study medication.

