#### **7.6. Concomitant Therapy**

##### **Treatment for Respiratory Disease**

Bronchodilators are allowed as prescribed. However, they should be withheld for the required time before spirometry as detailed in the MOP.

Other regular medications for treatment of airways disease (e.g., inhaled bronchodilators or inhaled corticosteroids) are permitted provided the subject has been on a stable dose for 1 month before baseline.

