# 3.4 General Study Design and Plan

This will be a multicenter, double-blind, randomized, placebo-controlled trial. One dose of Alvelestat (MPH966), 120 mg bid, will be tested against placebo. These doses are based on PK and PD modelling of Alvelestat (MPH966) inhibition of human neutrophil elastase.

The participants will be those patients with the AATD at risk for emphysema (Pi\*ZZ, Pi\*SZ, Pi\*null, or another rare phenotype/genotype known to be associated with either low [serum AAT level <11  $\mu$ M or <57.2 mg/dL] or functionally impaired AAT including "F" or "I" mutations)

Following a screening period of up to 4 weeks, patients will be dosed with study treatment or placebo for 12 weeks, with a subsequent 4-week follow-up period for safety and determination of the offset of the mechanistic effect of MPH966 on the primary endpoint (desmosine/isodesmosine).

The study is divided into 3 phases: a screening phase, treatment phase, and washout phase as detailed below:

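### SAP 7.4 puts a drug started more than 30 days before screening and still taken in neither the prior nor the concomitant medication class

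*SAP*

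**What the plan says.** SAP 7.4 defines two classes. On prior use: "Prior medications will be defined as medications started 30 days or more prior to screening visit and stopped any day prior to administration"; the administration meant is that of the first dose. On concomitant use: "Concomitant medications will be defined as medications started within 30 days prior to screening visit and ongoing"; the sentence then sets first dose as the time at which use must be ongoing, and adds drugs begun from that dose onward.

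The same section lists 15 drugs or classes to be checked yes/no at screening and follow-up. The list includes AAT augmentation, SABA, SAMA, LABA, LAMA and ICS, and is summarised by treatment and visit with no start-date condition. SAP 14.1 plans three tables on the Safety Set: Prior, Concomitant, and Concomitant COPD Medication. No definition other than the two in 7.4 is given for any of them.

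Four other rules determine which drugs participants bring into the trial:

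- **Augmentation** (Protocol 6.1, criterion 5b): participants "have received weekly infusions of augmentation at 60 mg/kg for at least 12 weeks prior to screening and intend to continue augmentation" for the duration of the study.
- **Airways drugs** (Protocol 7.6): other regular treatments are "permitted provided the subject has been on a stable dose for 1 month before baseline".
- **Hepatotoxic drugs** (Protocol 6.2, criterion 21, and 7.6): starting one in the 28 days before screening excludes the participant; established use of more than 28 days does not.
- **Timing** (SAP 3.4): "Following a screening period of up to 4 weeks", dosing begins.

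Protocol 7.6 also requires start and end dates for every drug taken at enrolment or during the study.

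**The concern.** Prior and concomitant classes should together cover every recorded drug, and what separates them is whether the drug was still in use at first dose. SAP 7.4 adds a start-date condition to both. Long-standing continuing treatment then has no class, although it is the background therapy a reader most needs to compare between arms.

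The stake is the reading of safety results. Liver function abnormalities belong to a primary safety endpoint. Protocol 5.8 says that transaminase rises in earlier alvelestat studies were confounded by alcohol or by other medication. The medication tables are where a reader would look for balance between arms in drugs that can raise liver tests. Outputs could also disagree: programmed as written, the Concomitant Medication table would show no eligible augmentation user while the by-visit checklist shows them all.

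**Working it through.** The plan states no figure to reproduce, so the check applies the two definitions to medication histories.

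**Notation.** Screening is day 0, S is the start day, E the last day of use, F the day of first dose. I assume that each drug is one record carrying the date it was first started, and that one month is 30 days. F = 7 and F = 28 are illustrative; 28 is the four-week limit in SAP 3.4.

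**Rules as written.**
- Prior: S ≤ −30 and E < F.
- Concomitant: (−30 ≤ S ≤ 0 and E ≥ F) or S ≥ F.

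**Result, identical for F = 7 and F = 28.**

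| Start | Use at first dose | As written | By use at first dose only |
|---|---|---|---|
| −84 (minimum augmentation history: 12 × 7) | ongoing | neither | concomitant |
| −365 (long-standing COPD drug) | ongoing | neither | concomitant |
| −31 | ongoing | neither | concomitant |
| −30 | ongoing | concomitant | concomitant |
| −10 | ongoing | concomitant | concomitant |
| −10 | stopped before | neither | prior |
| between 0 and F | ongoing | neither | concomitant |
| between 0 and F | stopped before | neither | prior |
| −60 | stopped before | prior | prior |
| after F | started later | concomitant | concomitant |

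The concomitant sentence can also be grouped so that the 30-day condition governs both branches. The branch for drugs begun on treatment then becomes impossible to satisfy, and the gap for older drugs remains.

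**Augmentation.** Eligible users have S ≤ −84 and intend to continue, so every one of them is unclassified.

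**Airways drugs.** Stability is counted from baseline, so a drug qualifies if S ≤ F − 30. It is concomitant if S ≥ −30. Both hold for S from −30 to F − 30, which is F + 1 start days:
- F = 28: days −30 to −2, 29 days.
- F = 7: days −30 to −23, 8 days.

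Continuing airways drugs started before day −30 are unclassified.

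**Hepatotoxic drugs.** Permitted established use means S ≤ −29. Concomitant needs S ≥ −30. Only starts on days −30 and −29 satisfy both; every earlier start with continuing use is unclassified.

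**Checklist coverage.** The 15 items include augmentation, the inhaler classes, roflumilast, theophylline, NSAIDs and acetaminophen. They do not include statins or anti-epileptics, both named in criterion 21, or tolbutamide and glimepiride, the CYP2C9 substrates named in Protocol 7.6.

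**The case against.** The best defence is that the key background drugs are reported by other routes. The by-visit checklist covers augmentation and the main inhaler classes. SAP 7.3 tabulates augmentation, and intent to continue it, by arm on the Safety Set. SAP 9.3.1 presents adverse-event data separately by augmentation, and SAP 6.3 and 10 plan analyses by augmentation. The primary model in SAP 8.1 takes augmentation as yes/no at enrolment. SAP 6.1 says that data will in general be listed, so the individual records should appear somewhere. No efficacy or safety analysis is stated to use the prior and concomitant classes.

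All of this stands, and it rules out two stronger readings. A reader might infer that the report would show almost no augmentation or maintenance therapy; the checklist and the AATD history table contradict that. A reader might also infer that all stable COPD therapy is lost. The stability rule runs from baseline, not from screening, so some qualifying drugs are correctly concomitant, and the documents give no proportion for the rest.

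The defence does not reach drugs off the checklist. For these, the Prior and Concomitant tables are the only planned summaries by arm; a listing gives no counts, and the checklist gives no dates or doses. A programmer may well ignore the written rule and use the customary one, but the SAP exists to make such derivations explicit.

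**Conclusion.** The two definitions are not exhaustive. Read literally, they omit from the Prior and Concomitant Medication tables:

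- all protocol-eligible augmentation;
- any continuing COPD drug started more than 30 days before screening;
- permitted established hepatotoxic drugs, apart from a two-day band of start dates;
- drugs started within 30 days before screening and stopped before first dose;
- drugs started between screening and first dose.

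The Concomitant COPD Medication table may inherit the gap. SAP 14.1 gives only its title, so it could instead be built from the checklist.

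The consequence is limited to descriptive safety-set tables. It would be wrong to infer that the primary test, its power or its augmentation adjustment is affected, since none of them uses these classes. The part that matters most is long-standing statins, anti-epileptics and similar drugs, because they bear on liver events and have no other summary by arm. How many participants take them cannot be told from the documents. The conclusion rests on the literal wording and on one start date per drug; infusion-by-infusion recording of augmentation would change which records drop out, but would not make the classes exhaustive.

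**What to change.** Replace the two sentences in SAP 7.4:

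- **Prior:** stopped before first dose, whatever the start date (E < F).
- **Concomitant:** ongoing at first dose, or started on or after it, whatever the start date (E ≥ F).

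Every drug then falls into exactly one class, as the last column of the table shows. Add a line saying whether the Concomitant COPD Medication table uses this definition or the checklist.

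The cost is a small text change, plus reprogramming if the tables are already coded. No new data are needed, because Protocol 7.6 already requires start and end dates. Sample size, type I error and the efficacy models do not change.

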# 7.5 Protocol Deviations

Protocol deviations will be summarized by treatment, site, and type of deviation; deviations that resulted in adverse and serious adverse events; and protocol deviations that resulted in termination.

A raw listing of all protocol deviations will be provided by treatment, site, subject ID, deviation date, resulting in AE, SAE, and termination; deviation description; reason for the deviation; deviation category; effect on product stability; and deviation resolution.

Finally, any subjects enrolled but not randomized will also be excluded from the analyses.

# 8 Efficacy Analyses

Analyses on all efficacy outcomes will be based on the 12-week period after randomization. Time periods included are baseline, Week 4, Week 8 and Week 12. Safety outcomes will include through Week 16.

Actual values, absolute change in actual values and the relative (percent) change from baseline will be summarised with descriptive statistics for continuous variables overall and by treatment arms. Relative (percentage) change will be calculated by:

[(Week or EndPoint value – Baseline Value) / Baseline value)] x 100%.

Baseline value will be computed as the last non-missing value prior to first study treatment dose at baseline visit (V1).

EndPoint will be computed as:

- Value at Week 12 for the completers (regardless of treatment compliance) or
- EOT value must be last non-missing post-baseline value for those that discontinue treatment before Week 12.

# 8.1 Primary Efficacy Endpoint Analyses:

The primary outcome is the relative change from baseline at week 12 in plasma desmosine/isodesmosine levels within treatment group. Within individual relative (percent) change from baseline in plasma desmosine/isodesmosine levels will be analyzed using Mixed Model Repeated Measures (MMRM). Relative change (percent) from baseline will be considered the response variable, with time as main independent fixed effect variable and baseline levels, augmentation, age, and smoking history (yes/no) as a fixed effect covariates, using an unstructured covariance matrix to model the within-subject errors. Available data from all time points will be included. The least squared estimates of the mean at each Week and EndPoint will be generated. [Note: Originally, it was planned to use sputum strata and FEV1 as covariates in the model. However, due to the restrictions of the pandemic, there was limited opportunity to collect the required sputum, and therefore will not be included in the analyses.] The analysis will be conducted using the SAS 'proc mixed', with the below specific code:

proc mixed data=Data; by TRTP; class SUBJID TRTP AVISIT AUGMENTATION SMOKING; model PCTCHG = BASE AVISIT AUGMENTATION AGE SMOKING; ddfm=KENWARDROGER; repeated AVISIT/ subject=SUBJID type=UN; lsmeans AVISIT / pdiff; run;

where PCTCHG is the relative (percent) change from baseline, BASE are baselines values, TRT is treatment arm, AVISIT is Weeks, AGE is age at enrollment, SMOKING is yes/no at enrollment and AUGMENTATION (yes/no) at enrollment. If imbalances are found between treatment groups in baseline characteristics deemed to be clinically important in influencing the relative change in the outcome, sensitivity analyses will be performed by including these variables as covariates in the above model. P-value<0.05 for the mean difference at Week 12 will be deemed significant. Estimate including 95% confidence interval of the least squares mean difference will also be provided.

If any issues related to convergence occur and cannot be resolved within the 'proc mixed', then alternative procedures will be considered (such as 'proc glimmix'). Other covariance structures will also be considered if convergence is an issue with unstructured covariance. Transformation of data or alternative distribution for the model will be considered should there be evidence of nonnormality of the data.

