# 3.5.3 Sample Size

Over the course of the study, target enrolment is 66 with the goal of 60 completers. Participants will be randomized in a 1:1 ratio to receive one of the following: 120mg Alvelestat (MPH966) BID or placebo. Randomization will be stratified by AAT genotype/phenotype.

The study will be powered for within-individual change in plasma desmosine/isodesmosine (DES) as the primary endpoint at Week 12 compared to baseline. A sample size of 30 participants in the MPH966 treatment group will give us >90% power to detect a 15% mean decrease of plasma DES from baseline to 12 weeks follow-up in patients treated with MPH966 (within subject change) using a two-sided paired t-test at  $\alpha$ =0.05. The calculation is based on an assumed correlation value of 0.5, baseline mean DES value of 0.466 and standard deviation of 0.09. This 15% mean decrease has been observed in trials of standard dose augmentation versus placebo (Ma S, 2013). A recent study of double dose versus single dose augmentation revealed a within subject decrease in plasma DES from 0.42 +/-0.03 ng/ml to 0.38 +/- 0.03 ng/ml (Campos MA, 2019). We will have >99% power to detect a comparable difference in DES in those who have Alvelestat added to augmentation if we assume their observed SD=0.03 and 85% power if we double their assumed SD, i.e., SD=0.06. Power will not be enough (~50%) to detect this difference if we use our original SD value of 0.9.

For comparing the mean change in DES between the two groups (placebo vs. MPH966), and assuming that there is no placebo effect over 12 weeks, a two-sided two sample t-test at  $\alpha$ =0.05 with a sample size of 60 (30 per group) reveals that we will have 82% power to detect a 15% difference in mean change in plasma DES.

By including a 10% attrition rate over 12 weeks, the required sample size is inflated to 66 (33 per group) to achieve the estimated powers. If we observe attrition rate less than we expected, we will have more statistical power to detect the expected differences. As one interim analysis will be conducted only for safety concerns (see Data Safety and Monitoring Plan), no adjustments to the Type I error are considered for estimating statistical powers.

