# 8.2 Secondary Efficacy Endpoint Analyses:

Percent change from baseline in the following outcomes at end of the treatment within patient and compared to placebo:

- 1. Plasma desmosine/isodesmosine (only relative change compared to placebo; within-individual change is the primary outcome)
- 2. Plasma Aa-Val-360
- 3. Serum NE activity
- 4. Plasma proteinase 3
- 5. Plasma cathepsin B
- 6. Plasma CRP
- 7. Plasma IL-6
- 8. Plasma IL-8
- 9. Plasma IL-1b

Plasma RANTES
 Plasma LTB4
 Plasma MMP9
 Plasma MMP12
 Plasma MPO
 Plasma PGP
 Plasma PK/PD (LCG/DDS)

The same approach, i.e., mixed modelling, will be used to analyse the change from baseline within and between treatments for the secondary outcomes using available data based on the schedule of collection and analyses. The analysis will be conducted using the SAS 'proc mixed', with the specific code given below. For each outcome, p-value<0.05 for pairwise comparisons of the least squared means between treatment groups will indicate treatment effect. This will be done for each outcome.

proc mixed data=Data; class SUBJID TRTP AVISIT SMOKING; model PCTCHG = BASE TRT|AVISIT FEV1 AGE SMOKING; ddfm=KENWARDROGER; repeated AVISIT/ subject=SUBJID type=UN; lsmeans TRTP\*AVISIT / pdiff; run;

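### The primary within-arm model adjusts for baseline DES, so the standard error of its Week 12 mean omits baseline sampling variation and the confidence interval is too narrow

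*SAP*

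**What the plan says.** SAP 8.1 defines the primary outcome as "relative change from baseline at week 12 in plasma desmosine/isodesmosine levels within treatment group". The code fits each arm on its own ("proc mixed data=Data; by TRTP") with the model line "model PCTCHG = BASE AVISIT AUGMENTATION AGE SMOKING" and requests "lsmeans AVISIT / pdiff". The text describes the same model, "with time as main independent fixed effect variable and baseline levels, augmentation, age, and smoking history (yes/no) as a fixed effect covariates", with an unstructured covariance and Kenward-Roger degrees of freedom. The decision rule is "P-value<0.05 for the mean difference at Week 12 will be deemed significant", reported with a 95% interval.

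The sample size in SAP 3.5.3 rests on a different analysis of the same quantity, "using a two-sided paired t-test". SAP 8.2 carries the modelling over to the secondary biomarkers: "The same approach, i.e., mixed modelling, will be used to analyse the change from baseline within and between treatments". Its code pools both arms and adds treatment-by-visit terms. SAP 6.6 promises two-sided 5% tests and 95% intervals.

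**The concern.** A least-squares mean from this model is evaluated at the sample mean of baseline DES. Its reported standard error reflects only the residual variation given baseline. If the trial were repeated, the baseline mean would also vary, and change depends on baseline, so the mean change varies more than the model reports.

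In a randomised comparison both arms share the same expected baseline and this term largely drops out. In a one-arm estimate it stays. Kenward-Roger also conditions on the covariates, so it does not help. The paired t-test behind the sample size has the right variance; the model that replaced it does not.

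At stake are the width of the primary interval and the error rate of the primary test. Neither document specifies an unconditional standard error, a bootstrap or an unadjusted test, either as the primary analysis or as a check.

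**Working it through.** **Inputs.** SAP 3.5.3 gives 30 patients in the active arm, baseline mean 0.466, SD 0.09, correlation 0.5, a 15% fall and two-sided 5%. Other values of r, and all class splits, are assumptions.

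**1. The plan's own figure.** Difference = 0.15 × 0.466 = 0.0699. SD of change = 0.09 × √(2(1 − 0.5)) = 0.09. Noncentrality = (0.0699/0.09) × √30 = 4.25. Paired t power is 98.4%, which agrees with the stated >90%.

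**2. Mechanism, on absolute change.** Let X be baseline, C the change, s the common SD.
- Var(C) = 2s²(1 − r) and Cov(C, X) = −s²(1 − r).
- The share of Var(C) explained by baseline is R² = (1 − r)/2.
- The model variance of the mean is Var(C)(1 − R²)/n; the sampling variance is Var(C)/n.
- The ratio of standard errors is √(1 − R²) = √((1 + r)/2), which is 0.866 at r = 0.5.

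**3. Percent change, the planned scale.** Week 12 analysis of covariance with baseline, augmentation, age and smoking, balanced classes, n = 30, 20,000 simulated trials per row:

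| r | Mean DES | True mean % change | R² on baseline | Model SE / true SD | Coverage, SAP covariates | Coverage, one-sample t |
|---|---|---|---|---|---|---|
| 0.3 | no change | +2.9 | 0.36 | 0.785 | 88.6% | 94.9% |
| 0.5 | no change | +2.1 | 0.26 | 0.841 | 90.8% | 94.8% |
| 0.7 | no change | +1.3 | 0.16 | 0.897 | 92.8% | 94.9% |
| 0.9 | no change | +0.4 | 0.06 | 0.955 | 94.0% | 94.8% |
| 0.5 | 15% fall | −13.5 | 0.15 | 0.906 | 92.7% | 94.8% |

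At r = 0.5 with no change, the model reports a standard error of 3.26 percentage points against a true value of 3.88; the one-sample analysis reports 3.82.

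**4. The repeated-measures model itself.** REML, unstructured covariance, three visits, 1,500 trials, no change in mean DES: model standard error 3.27 against an empirical 4.05, with coverage 89.8% against 93.9% for the one-sample t. The Week 12 versus Week 8 contrast, which is what the pdiff option prints, rejected 4.9% of the time. The common baseline slope cancels there, but that contrast does not test change from baseline.

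**5. Unbalanced classes.** Default least-squares means weight the levels of augmentation and smoking equally, whatever their frequencies. This adds variance and dilutes the understatement. With assumed 70/30 and 80/20 splits, coverage was 92.3% to 93.3% in separate runs with no change in mean DES, and about 94% at a 15% fall. At those splits, power of the SAP model for a 15% fall dropped to 81%, against 93% for the one-sample t.

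**6. Direction of the errors.** Percent change is a ratio, so its mean is above zero even when mean DES is unchanged: to first order (1 − r)(SD/mean)² = 0.5 × (0.09/0.466)² = 1.9%, and 2.1% by simulation. In that setting the model rejected zero in 12.6% of trials and the one-sample t in 6.5%, mostly as increases. Rejections in the direction of benefit were 1.3% to 1.9% across simulations, below the nominal 2.5%. When the true mean percent change was set to about zero (balanced classes), the two-sided error was 9.0% against 5.1%.

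**7. After the fix.** With complete data, percent change fitted on visit alone reproduces the one-sample analysis at Week 12: coverage about 95%, and power for a 15% fall 93.4%.

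**The case against.** Several points on the other side stand in part.

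- **Which output is primary.** The code prints visit-versus-visit differences, whose error is nominal. The point depends on reading the primary p-value as the Week 12 mean against zero. That is the only reading that tests a change from baseline, but the SAP does not say so.
- **A conditional target.** The model standard error is valid for the mean at exactly the observed baselines. The SAP does not state that target.
- **Planning assumption.** The size depends on r = 0.5. At r = 0.9 coverage is already about 94%.
- **Signal-seeking study.** SAP 6.6 describes it that way, and the planned descriptive means and SDs would let a reader rebuild an unadjusted interval. This limits the harm, but the declared primary test would still be the adjusted one.
- **Baseline adjustment is in the protocol.** Protocol 10.3.1 uses baseline as a covariate, but to compare treatment groups, where it is sound. It does not justify the one-arm standard error.

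A reader might also infer that the adjusted mean always equals the raw arm mean. That holds only with complete data and balanced classes. A reader might infer that every within-arm secondary result is distorted equally. The SAP 8.2 code pools the arms and evaluates at the pooled baseline mean, which roughly halves the omitted term: error about 7.1% on absolute change if r = 0.5, against 9.0% in a single-arm fit. The documents give no r for those biomarkers.

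**Conclusion.** The point holds for the Week 12 least-squares mean, its interval and its test against zero in the alvelestat arm. At the plan's inputs the nominal 95% interval on percent change covers about 91% (no change in mean DES) to 93% (15% fall) with balanced classes, and about 92–94% with assumed 70/30 and 80/20 splits. A one-sample t gives about 95%. The gap narrows as r rises. The between-arm contrasts in SAP 8.2 are largely unaffected.

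Two stronger readings are not supported. A reader might take the 12.6% rejection rate with no change in mean DES as a false-positive rate caused by the standard error. Part of it is correct detection of a true mean percent change of about +2.1%. A reader might also conclude that the plan inflates false claims of benefit. With no change in mean DES, the excess rejections on the planned percent scale are mostly false increases. The main harm is an interval that is too narrow, which matters for a borderline result. The stated >90% power is not overturned.

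**What to change.** In SAP 8.1, fit percent change with visit as the only fixed effect, keeping the unstructured covariance. Remove baseline and the equally weighted class covariates from this within-arm model. Name the Week 12 least-squares mean against zero in the alvelestat arm, with its 95% interval, as the primary test, and state that the visit-to-visit differences are not that test.

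Alternatively, keep the covariates and replace the standard error with one that includes baseline sampling variation, for example a bootstrap that resamples patients.

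Keep baseline as a covariate in the between-arm model of SAP 8.2. Do not move Week 0 DES into the response vector: percent change at Week 0 is zero for everyone, so this would require raw DES as the response and would change the primary endpoint.

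The cost is a short edit to text and code before unblinding, plus a line in SAP 10. The standard error becomes slightly larger when the classes are balanced. Power for a 15% fall stays at about 93%, so the >90% statement in SAP 3.5.3 holds.
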